This will be a telephone call scheduled 10 days (+ 4 days) by a clinical research staff member to review blinded CGM data for the purpose of logging CGM parameters including average glucose with standard deviation, time in range, percent highs, percent lows, and severe lows, and days with CGM data. If the CGM is worn less than 60% of the time, the participant may be withdrawn from the study at the discretion of the study investigator. Each participant, with the help of a guardian, will insert a non-blinded sensor according to the Dexcom G6 user guide, connect the Dexcom to a compatible phone, and activate the share functions with the clinic. If the guardian is not able to set-up the Dexcom at home, the patient and guardian will be asked to come for Visit 2B within 5 days to have the non-blinded Dexcom set-up in clinic and assure that inserting the CGM is a skill that could be done independently. If the guardian or participant cannot demonstrate that they can set-up the CGM system independently, the participant will be withdrawn from the study.

Between Visit 2T and Visit 3, clinic research staff will actively monitor the participants' blood glucose levels remotely through an Apple iPad. Currently available commercial Dexcom software is able to monitor up to 10 devices on a single iPad, and we plan to have two iPads

throughout the study period. Active remote monitoring of CGM data will occur during 7 days per week between 8:00 AM and 8:00 PM.

The goal of the secure text messaging is to provide supervision and feedback to the adolescents that is supportive and collaborative, with the ultimate goals of increasing self-efficacy and improving diabetic self-management skills. The intention is not to make the texting platform cumbersome and to allow the participants freedom in making lifestyle choices that will not interfere with their diabetes control. Only reactive texts and coaching texts will be sent during the school hours.

Participants will still be able to use normal clinic communication methods through the electronic patient portal and diabetes telephone emergency line as usual. Participants will be free to optimize their treatment independently as previously educated about trend management. We will provide a letter for school indicating that the participants are a part of a study and they have to carry their cell phones with them and respond to text messaging from us.

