We will utilize texting interventions as described in the Novel Interventions in Children's Healthcare (NICH) program¹³ which was a recent study that implemented texting interventions for participants with uncontrolled diabetes. Texts will be sent in the following categories:

- Reminding: this will include texts to request or prompt the participant or the parent for a reminder or an immediate diabetes related actions. The following situations are **immediate situations** that require immediate mandatory reminder text from the research staff:
 - If blood glucose level is above 300 mg/dL for more than 2 hours, the research staff will send a text to remind about action regarding insulin. One possible example text is as follows: "I have seen that you have constant highs ↑↑↑ since last night. Did you get your Lantus last night? Please check ketones and let me know so we can help dose your insulin (syringe emoji)". Insulin dosing recommendations will be provided according to clinic established protocols for managing hyperglycemia with or without ketones.
 - If blood glucose is below 70 mg/dL for more than 10 minutes with double arrows down, a text will be sent to treat a low. One possible example text will be as follows: "your CGM is reading that you're 63. Time for some carb snack to treat that low (cookie Emoji)"
 - If there is no CGM data for 4 hours, a text will be sent. An example text is as follows: "Is your Dexcom working? I cannot see any numbers from my end".

If a reactive text has not been responded to within 30 minutes, the research staff will attempt to call guardian or contact school to get the issue resolved.

In addition to the reactive texts, reminders can also include messages to remind of regular diabetes tasks, such as "It's Lantus time. Don't forget it please (smiley emoji)". Log reminders will also be sent "It will be easier for us "and you" if you enter how much insulin you have received. Can you please enter your insulin doses in Dexcom (target emoji)?"

Research staff will coordinate a "trend review time" every 7 days (+/- 3 days) to walk through glucose trends and insulin adjustments necessary. Example texts will include

“time for some trend review... seems that you’ve been having high blood sugars after your breakfast literally every day. I think you’re currently dividing your carbs by 12 for breakfast. I suggest that we change that to 1:10 to give you more insulin...”.

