Reminder texts will also be sent to remind participants and guardians about upcoming research Visit appointments.

- Reinforcing. Texts will provide encouragement and reinforcement for adherence to diabetes related tasks. Examples will include texts stating “(screenshot image from the participant’s glucose trend), followed by “awesome control! Keep it up!”.
- Coaching. Texts in this category will include response to participants and guardians’ complaints and questions. They could include management of participant or guardian questions about abnormal blood glucoses or ketone management interventions. Clinic protocols to manage sick days will be utilized.

All Tigertext communication will be stored electronically in a secure shared file. It will be used to retrospectively calculate time invested by clinical staff, and analyze percentage of texting category used.

First Follow-up, Visit 3

This visit will be scheduled 11-12 weeks (+/- 5 days) after Visit 2B or visit 2T. Adverse events, insulin doses and concomitant medications will be reviewed by study staff. Height and weight will be measured, and a physical exam will be performed. A capillary blood sample will be obtained for HbA1c determination. CGM reports will be analyzed. Participants will complete the PHQ-9A, PEDS-QoL4, Collaborative Parent Involvement Scale, and SEDM.

If due to participant or family scheduling conflicts, the participant is unable to complete a clinic visit for Visit 3, then they can participate in a telemedicine visit. Participants will be requested to measure height and weight at home. A physical exam will be performed as fully able within the telemedicine platform. HbA1c will be obtained with other standard of care labs. CGM report analysis will not be affected by the telemedicine visit. Surveys for PHQ-9A, PEDS-QoL4, Collaborative Parent Involvement Scale, and SEDM will be sent via MyChart to the participant’s parent to be completed by the participant. Parents will send images of the completed surveys to the research team via MyChart.

We will discuss the next phase of the study during that visit. We will emphasize that the research staff will not monitor CGM data remotely, that research staff will not be real-time followers of their CGM data, and they will not be able to use TigerText to communicate with our clinic anymore. They will be encouraged to continue the activated alarms to allow for self-control.

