Collaborative Parent Involvement Scale		X		X	X

[figure not shown]

Figure 1. Timeline for study. Study visits are denoted by arrows. A timescale in months is below the timeline; there is not a specified interval between Visits 1 & 2.

Participant withdrawal criteria

The following study withdrawal criteria will apply:

1. Participants can terminate involvement in the study at any time point without any repercussions.
2. If data on the CGM is available < 60% of the time worn, patient may be withdrawn at the discretion of the research investigator.
3. If pregnancy occurs during study period.
4. Allergic reaction to adhesive surface of CGM sensor

Primary endpoint

The primary outcome is change in Hemoglobin A1c (HbA1c) between the baseline visit (Visit 2) and three-month follow-up visit (Visit 3) after active remote monitoring and secure text messaging.

A 5% significance level will be used to declare statistical significance for the primary outcome comparison.

Exploratory endpoints

- Change in Peds PHQ-9A, PED-QOL4A, SEDM, and Collaborative Parent Involvement Scale scores.
- Time taken for a text to be read by participant and guardian.
- Time spent by medical provider per participant per day.
- The difference in A1c between clinical remote monitoring HbA1c (Visit 3) and self-monitoring utilizing CGM (Visit 4)
- The difference in A1c from baseline (Visit 2) and after the two phases of the study intervention (Visit 4).
- The following outcomes will be compared between baseline, three months and six months using repeated measures ANOVA as follows:
 - Time spent in the target glucose range from 70–180 mg/dL
 - Time spent below target glucose 70 mg/dL

- Time spent above target glucose 180 mg/dL
- Average of time the participants wore the CGM

Statistical Plan

Paired sample t-tests will be used to assess continuous variable differences between two time points. Generalized linear models will be run to identify items in medical and social histories that could predict hemoglobin A1c, the primary outcome. Point estimates will be reported with 95% CIs.

As this is a pilot exploratory study, we will implement per-protocol analysis and not an intention-to-treat analysis. Only patients who have completed the three phases of the study will be included for analysis.

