The informed consent and HIPAA permission obtained from the subject's legally acceptable representative includes explicit consent for the processing of personal data and for the investigator to allow direct access to his or her original medical records for study-related monitoring, audit, IRB review, and regulatory inspection. This consent also addresses the transfer of the data to other entities and to other countries.

For any telemedicine visits completed, verbal consent to perform a telemedicine visit will be obtained from the participant's parent/legal guardian/legal representative. All telemedicine visits will be completed using Children's Health telemedicine platform.

The subject's legally acceptable representative has the right to request through the investigator access to the subject's personal data and the right to request rectification of any data that are not correct or complete. Reasonable steps will be taken to respond to such a request, taking into consideration the nature of the request, the conditions of the study, and the applicable laws and regulations.

Disclosure to outside entities

All data, whether electronic or hardcopy, will be referenced to a unique patient identifier, with subjects' identifying information kept in separate secure files. The following entities will be granted access to some or all data and specimens from this study:

- The UT Southwestern Institutional Review Board (IRB).
- Dexcom, Inc.
- Representatives of other governmental and regulatory agencies.

Data and Safety Monitoring Plan

This study represents minimal incremental risk over routine care for children with type 1 diabetes. Accordingly, a separate DSMB is not indicated.

ClinicalTrials.gov

We will register the study with ClinicalTrials.gov prior to enrolling any subjects.

Adverse event reporting

No investigational drug or device will be used in these studies, and consequently adverse event reporting, *per se*, is not applicable. However, we will monitor as secondary outcomes hypoglycemia frequency, DKA admission risk, and report all study adverse events.

Budget: \$37,300 (Dexcom, Inc will provide the CGM devices for the study)

Certified Diabetes Educator time - 36 hours per week \times 20 weeks of study \times \$50 per hour = \$36,000

iPad devices for monitoring CGM data – 2 devices \times \$350 per iPad _____ = \$700

Patient incentive gift cards – \$10 \times 3 visits \times 25 participants) _____ = \$600

[figure not shown]

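### The exploratory provider-time endpoint has one stated source, the text-message archive, which misses screen monitoring, phone calls and off-text data review, so it will probably understate provider time.

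*Combined protocol and SAP*

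**What the plan says.** The endpoint is a single line under Exploratory endpoints: "Time spent by medical provider per participant per day". It names no component activities and no method of calculation.

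The method, so far as there is one, is in the Schedule of procedures, at the end of the description of text categories and just before First Follow-up, Visit 3. There, "All Tigertext communication will be stored electronically in a secure shared file", and then "It will be used to retrospectively calculate time invested by clinical staff, and analyze percentage of texting category used".

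The same part of the protocol describes work that is not texting:

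- **Screen monitoring.** Under Telephone or Clinic Follow-up, Visit 2B or 2T: "Active remote monitoring of CGM data will occur during 7 days per week between 8:00 AM and 8:00 PM". The software is "able to monitor up to 10 devices on a single iPad, and we plan to have two iPads".
- **Calls.** When a reactive text has had no reply within 30 minutes, "the research staff will attempt to call guardian or contact school to get the issue resolved".
- **Trend review.** Staff go through glucose trends and insulin adjustments with the participant every 7 days (+/- 3 days). The protocol illustrates this with sample texts.

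The Budget section funds "Certified Diabetes Educator time - 36 hours per week" for 20 weeks.

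**The concern.** The title includes feasibility, and this is the only endpoint that measures staff burden. A clinic deciding whether it could run such a service would look to it for the staffing cost. The Budget points the same way: educator time is $36,000 of the stated $37,300, about 97%.

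If staff time is rebuilt from messages, a participant whose feed is watched all day but who triggers no text adds nothing to the figure for that day. Calls are made when a reactive text goes unanswered, so the omission may fall unevenly, with more time lost for the participants who are harder to reach. Minutes of calling and chart reading that are not noted at the time cannot be reliably recovered later.

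Because there is also no rule for converting messages to minutes, the reported value would depend on a choice made after the data are in.

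**Working it through.** The documents give no expected value, SD or precision for provider time, so there is no planned figure to reproduce. The check has two parts.

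**1. Which activities leave a trace in the archive?**

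| Activity | Where described | In the text archive? |
|---|---|---|
| Reminding, reinforcing and coaching texts | Text categories, Visit 2B/2T section | Yes |
| Weekly trend review, the exchange itself | Same | Yes, where held by text |
| Reading CGM data before that exchange | Same; weekly review also in Overview of methodology | No |
| Calls to guardian or school | Same | No |
| Watching CGM feeds, 8 AM to 8 PM daily | Same; also Overview of methodology | No |

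No time log, call log or roster record appears in Data management (which covers CGM reports), the table of assessments or the Statistical Plan.

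**2. How large could the gap be?** This is for scale only.

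Formula: minutes per participant per day = (hours per week x 60 / 7) / number monitored at once.

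Inputs from the documents:
- Coverage: 12 h x 7 d = 84 h per week.
- Budgeted educator time: 36 h per week, which is 36/84 = 43% of coverage.
- Stated monitoring capacity: 2 iPads x 10 devices = 20 at once.

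Results:

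| Monitored at once | Coverage, min per participant-day | Budgeted educator time, min per participant-day |
|---|---|---|
| 20 | 84 x 60 / 7 / 20 = 36.0 | 36 x 60 / 7 / 20 = 15.4 |
| 10 | 84 x 60 / 7 / 10 = 72.0 | 36 x 60 / 7 / 10 = 30.9 |

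Assumption, not in the documents: 3 to 10 staff texts per participant per day at 0.5 to 2 minutes each. Text time is then 3 x 0.5 = 1.5 minutes to 10 x 2 = 20 minutes.

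With 20 monitored:
- Share of coverage time: 1.5/36.0 = 4% to 20/36.0 = 56%.
- Share of budgeted educator time: 1.5/15.4 = 10% to 20/15.4 = 130%.

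The second range passes 100%, which shows how little the documents constrain the answer. Coverage hours are also an upper bound on attention, since staff on cover need not be looking at a screen throughout.

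**The case against.** The strongest reply is that this is one undefined line in a list of exploratory endpoints. The primary outcome is HbA1c change, and no threshold or go/no-go rule rests on provider time. That stands, and it limits the weight of the point. A reader might infer from the title that provider time is the trial's main feasibility measure. The documents do not say so: they rank no feasibility measure, and time to read a text and CGM wear also bear on feasibility.

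Second, the plan does not exclude other sources. A reader might infer that staff time will come from texts and nothing else, but that rests on silence. It also needs the step from clinical staff in the Schedule of procedures to medical provider in the endpoint, which is reasonable but not stated. If another source exists, one sentence would name it.

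Third, a reader might conclude that weekly trend review is left out altogether. It is not, because the protocol's own examples of it are texts. Only the preparation off the messaging platform is missed.

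Fourth, understatement is not certain. A rule that counted from first to last timestamp in a conversation would include idle time and could push the figure up. This softens the direction but does not rescue the endpoint: calls and screen time would still not be measured, and the result would depend on an unstated rule.

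Fifth, coverage is not the same as work. Mandatory alarms are set for followers, and replies trigger an alert on the staff phone, so part of the 84 hours may be availability. The 36 budgeted educator hours do not settle this, because fellows and nurse practitioners may also monitor. So coverage should not be counted as workload.

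**Conclusion.** The point holds for an exploratory endpoint. The one source the plan names for provider time cannot record three kinds of work that the plan itself requires, and no conversion rule is given. Followed as written, the plan would report something close to texting time under the name of provider time, and that figure will probably be too low.

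The direction is probable, not certain. It rests on no other source being used and on a conversion rule that does not credit idle time. The size cannot be fixed from the documents. The 4% to 56% of coverage time and 10% to 130% of budgeted educator time depend wholly on the assumed number and length of texts and on 20 being monitored at once. They should not be quoted as estimates of bias. The primary analysis is unaffected.

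**What to change.** In the protocol, define the endpoint and its sources:

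1. On-duty staff log, per shift, the minutes spent on calls, on off-text review of CGM data and on active screen checking, by participant where practicable.
2. Fix in advance the rule that turns message timestamps into minutes, including how gaps within a conversation are treated.
3. Report provider time as texting time plus logged non-text minutes, showing the parts and the total, with no minute counted twice.
4. Report rostered coverage (84 h per week, with the number monitored) separately as availability. Do not add it to the total: texts, calls and reviews made on shift would be counted twice, and the per-participant figure would move with enrolment alone (36 minutes at 20 monitored, 72 at 10, for the same roster).
5. If no log is kept, label the archive-only figure texting time.

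The cost is protocol wording, a minute or two of logging per shift by staff already on duty, and probably a less favourable workload figure. Visits, treatment and the primary analysis do not change.

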Schedule of procedures

Screening, Visit 1

Screening visit. It will include review of inclusion and exclusion criteria and obtaining informed consent from legal guardians and assent from participants. The visit is expected to take around one hour. The visit can be combined with Visit 2.

Participants will be recruited from either an endocrinology inpatient floor or the outpatient clinic.

Baseline, Visit 2

The visit will include review of diabetes history including current doses, prior hospitalizations, previous complications, and detailed medical and social histories and a complete physical examination that will include measurement of height and weight. A capillary blood sample will be obtained for HbA1c determination using the Alere Afinion device. A HbA1c from within two weeks of Visit 2 may also be used. A urine pregnancy test will be performed on females capable of becoming pregnant.

Participants and guardians will be introduced to the concept of a continuous glucose monitor in general, with specific details about how to apply, use, and share the Dexcom G6 data. Mandatory alarms will be set for participants and followers for blood glucose below 70 mg/dL, blood glucoses above 250 mg/dL, “urgent low soon”, “signal loss”, and “no reading” alerts. Participants may set extra alarms to personalize their diabetes alerts. Participants will also be taught to log their food and insulin intake into the CGM device.

Participants will complete the PHQ-9A, PEDS-QoL4, Self-Efficacy for Diabetes Self-Management measure (SEDM) questionnaire, and Collaborative Parent Involvement Scale. A blinded CGM will be placed on the participant with the goal to obtain baseline data for 10 days. A test secure text message will be sent through TigerConnect to guardian and participant, and they will be introduced to the messaging platform used. We will determine with the participants and parents their preferred contact hours and school hours to allow texting for non-urgent matters to be done at convenient times. This visit will take up to 2 hours.

Between Visit 2 and Visit 2T, participants and clinical staff will be notified if there is signal loss from the blinded CGM. Dexcom, Inc. will provide troubleshooting of the blinded CGM if any technical issues arise. Participants will be asked to continue taking care of their diabetes as usual and will not have access to the CGM data.

Telephone or Clinic Follow-up, Visit 2B or 2T

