We will utilize the Collaborative Parent Involvement Scale¹¹, a 12-item questionnaire with a five-point Likert scale, from almost never to always, and is targeted for adolescents. The scale aims to assess parental use of problem solving, teachable moments, diabetes, help with autonomy, and supervision of diabetes care when the adolescent is not around.

TigerConnect

TigerConnect is a secure messaging application approved by many large healthcare organizations, including Children’s Medical Center Dallas, to allow for secure exchange of Protected Health Information (PHI) that is compliant with HIPAA. It allows sharing texts, emoji, images and videos.

We will utilize the TigerConnect platform to communicate with participants and guardians. A participant receives a text message alert that a new secure message was sent, with a clickable hyperlink provided to check the contents. The hyperlink opens in the phone’s default browser, directs the participant or guardian to the encrypted secure chatting window, and allows direct communication with research staff. When a participant or parent replies to the window, an alert is sent to the research staff’s phone and to an open webpage that has the chat open.

Estimated study duration

Study duration for participants

The duration of the study for participants from Visit 2 until Visit 4, the final study visit, is approximately 6-7 months.

End of study

The study will end with Visit 4 of the last subject.

	Screening Visit (1)	Baseline Visit (2)	Telephone/Clinic Follow-up (2T/2B)	First Follow-up visit (3)/(Potential telemedicine visit)	Second Follow-up visit (4)/ /(Potential telemedicine visit)/EOSV
Consent	X				

Inclusion/Exclusion					
Demographic Information	X				
Full physical exam		X		X (or telemedicine exam if telemedicine visit)	X (or telemedicine exam if telemedicine visit)
Vital signs		X		X (not applicable for telemedicine visit)	X (not applicable for telemedicine visit)
Height and Weight		X		X	X
Hemoglobin A1c		X		X	X
Urine pregnancy test		X			
Blinded continuous glucose monitor placement		X			
Un-blinded continuous glucose monitor placement			X		
Education about continuous glucose monitor use and placement		X	X		
Review of CGM data			X	X	X
Establishing messaging platform with patient and parent		X			
Patient Health Questionnaire (PHQ-9A)		X		X	X
Pediatric Quality Life Inventory for teens 13-18, PedsQL4.0		X		X	X
Self-Efficacy for Diabetes Self-Management measure (SEDM)" questionnaire		X		X	X

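### At telemedicine Visits 3 and 4 the parent receives and returns the adolescent's questionnaires, including the scale on parental behaviour and the depression screen, which may shift exploratory change scores

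*Combined protocol and SAP*

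**What the plan says.** **Follow-up.** Under First Follow-up, Visit 3, a family with a scheduling conflict has a fallback: if "the participant is unable to complete a clinic visit for Visit 3, then they can participate in a telemedicine visit". For that case the protocol states: "Surveys for PHQ-9A, PEDS-QoL4, Collaborative Parent Involvement Scale, and SEDM will be sent via MyChart to the participant’s parent to be completed by the participant". The return route is: "Parents will send images of the completed surveys to the research team via MyChart". The section Second Follow-up, Visit 4/EOSV gives the same procedure.

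**Baseline.** Under Baseline, Visit 2: "Participants will complete the PHQ-9A, PEDS-QoL4, Self-Efficacy for Diabetes Self-Management measure (SEDM) questionnaire, and Collaborative Parent Involvement Scale". Visit 2 includes a physical examination, a capillary sample and sensor placement. Neither its description nor the schedule table gives it a telemedicine option. The text does not say who is in the room or who handles the forms. The place may also vary: "Participants will be recruited from either an endocrinology inpatient floor or the outpatient clinic", and of the screening visit it says "The visit can be combined with Visit 2".

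**Instruments.** Of the Collaborative Parent Involvement Scale, which the adolescent answers, the protocol says: "The scale aims to assess parental use of problem solving", among other parental behaviours. The PHQ-9A is the depression screen.

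**Endpoints and analysis.** The exploratory endpoints include "Change in Peds PHQ-9A, PED-QOL4A, SEDM, and Collaborative Parent Involvement Scale scores". The Statistical Plan compares continuous variables between two time points by paired t-test, in participants who complete all three phases. Study design states that there is no control group. Nothing in the plan provides for private completion, a direct return route, recording of how the forms were collected, or analysis by mode.

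**The concern.** A parent who has to photograph and send a form handles the answers on it, and the adolescent can foresee this. Two of the four instruments are sensitive to that. One asks the adolescent to report on the parent's own behaviour, and the other asks about depressive symptoms. The plausible direction is towards kinder ratings of the parent and fewer reported symptoms. That direction is an inference, but it is also the direction in which the intervention would appear to help. The argument is weaker for PedsQL and SEDM, which do not rate the parent.

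The parent route exists only after baseline, so a shift in the answers can enter the change from Visit 2 and need not cancel. A single-arm design has no comparison group in which the same shift would show up. A paired t-test on the pooled visits would count it as change over time.

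What is at stake is the reading of the exploratory questionnaire results, together with the confidentiality of the adolescent's answers on mood and family.

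**Working it through.** **The plan's own figure.** The only power calculation concerns HbA1c: SD 1.5%, change 1%, alpha 0.05, power 80%, n = 18. Treating 1.5% as the SD of the paired change and the test as two-sided, the normal approximation gives

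n = ((1.960 + 0.842) × 1.5 / 1)² = 17.66, rounded up to 18.

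The figure reproduces. It says nothing about the questionnaires, for which the documents give no SD, target difference or power.

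**The two collection routes side by side.**

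| | Visit 2 | Visits 3 and 4 in clinic | Visits 3 and 4 by telemedicine |
|---|---|---|---|
| Who answers | Adolescent | Adolescent | Adolescent |
| Who receives the blank forms | Not stated | Not stated | Parent |
| Who returns the completed forms | Not stated | Not stated | Parent |
| Private completion required | No | No | No |

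The documents establish that the parent is the required recipient and sender in the last column only. They do not establish that the parent could not see the answers in the other two.

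**Size of a possible bias.** Let f be the share of analysed participants whose follow-up visit is by telemedicine. Let s be the mean shift that the parent route causes relative to baseline conditions, in SDs of the change score. Then

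bias in mean change = f × s.

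Neither f nor s is in the documents. I assume f from 0 to 50% and s from 0 to 0.5 SD. Both ranges include zero, because telemedicine is only a fallback and because parents may have seen the baseline answers too.

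- Lower end: f = 0 or s = 0 gives a bias of 0.
- f = 25%, s = 0.2: 0.25 × 0.2 = 0.05 SD.
- f = 25%, s = 0.5: 0.25 × 0.5 = 0.125 SD.
- Upper end: f = 50%, s = 0.5: 0.50 × 0.5 = 0.25 SD.

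**Scale for comparison.** The mean change detectable with 80% power by a two-sided 5% paired t-test (noncentral t) is 0.701 SD at n = 18 and 0.584 SD at n = 25. The plan sets no such benchmark for the questionnaires; it is used here only for scale. The upper-end bias is 0.25 / 0.701 = 36% of it at n = 18 and 0.25 / 0.584 = 43% at n = 25. The lower end is 0%.

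**False-positive rate.** If the true change is zero and the mean is shifted by f × s, ignoring any extra variance from mixing modes, the nominal 5% test rejects as follows:

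| Bias (SD of change) | n = 18 | n = 25 |
|---|---|---|
| 0 | 5.0% | 5.0% |
| 0.05 | 5.5% | 5.7% |
| 0.125 | 7.9% | 9.2% |
| 0.25 | about 17% | about 22% |

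The possible effect therefore runs from nothing to material, and the documents do not say where in that range the trial lies.

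**The case against.** **The baseline contrast is not proven.** A differential bias needs answers that the parent could see less readily at baseline than at follow-up. Guardians take part in Visit 2, and the protocol does not say that the adolescent answers alone there. A reader might infer that baseline was private and always in the clinic. The documents support neither: they support in person, possibly on the inpatient floor, with nothing said on privacy. This objection stands, and it is why the range starts at zero. It does not remove the point, because only the telemedicine procedure makes the parent the required handler of the completed forms.

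**Bias is a risk and not a finding.** The forms are still meant to be filled in by the adolescent. That the parent reads them, that the adolescent expects this, and that the answers then move are all inferences. A reader might take the procedure as proof that the change scores are biased, but the text does not go that far.

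**The upper figures rest on two assumptions taken at their upper ends.** It would be tempting to say that some 40% of a detectable effect could be artefact. That pairs the highest assumed share with the highest assumed shift, and neither has support in the documents. At a 25% share and a 0.2 SD shift, the false-positive rate at n = 18 is 5.5%. This objection stands.

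**The endpoints are exploratory.** The study is an uncontrolled pilot, and other sources of change cannot be separated from the intervention either. That is true and limits the weight of the point. It is no reason to keep a further source that is cheap to remove.

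**Conclusion.** The point holds as a risk of bias, and as an avoidable weakness in confidentiality, that the plan neither prevents nor records. At telemedicine Visits 3 and 4 the parent receives and returns the questionnaires, among them the scale on parental behaviour and the PHQ-9A; no such route is specified at baseline. Without a control group or a record of mode, any resulting shift would be indistinguishable from an intervention effect.

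The size cannot be fixed from the documents. Under the assumed ranges it is 0-0.25 SD of change, or 0-36% of the detectable effect at n = 18 and 0-43% at n = 25. A favourable direction is plausible, chiefly for the two instruments named, but it is not shown. The primary HbA1c endpoint and the sample size are not affected.

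**What to change.** In the telemedicine paragraphs for Visit 3 and Visit 4:

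1. Replace return by the parent with completion and submission by the adolescent. This can be done through a secure link on the adolescent's own phone, or during the video visit with the parent out of view. The inclusion criteria already require a smartphone with internet access.
2. Ask for the same private completion at in-person visits, including Visit 2, so that conditions match before and after.
3. Record the mode of completion at each visit.
4. In the Statistical Plan, add a descriptive sensitivity analysis that reports the change scores for in-person visits only, beside the full set.

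The cost is protocol wording and the set-up and approval of a survey link. The study's text messaging channel closes to participants after Visit 3, so it could not carry the Visit 4 forms. The sensitivity analysis will be imprecise at this sample size and should be read as description and not as a test. If forms have already been returned by parents, recording which visits these were still allows that analysis.
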